The T2 (mid-intervention) assessments are made because some patients may be too sick to complete the 7-session intervention. For these patients, we will use the T2 assessment to represent the most available data on intervention effect.

Sample size and statistical power considerations:

Two important hypotheses need to be established in this trial: 1) IMCP is superior to EUC; and more importantly, 2) IMCP is superior to ISP for improving psychosocial outcomes in patients with advanced cancer. Therefore, we have based sample size considerations on sufficient statistical power to detect these two differences. We have conservatively based our sample size calculations on a 0.20 standardized mean difference in the MANOVA canonical variates between the IMCP and ISP interventions. This 0.20 difference is what Cohen would consider a —small effect size in psychosocial research (Cohen, 1992), representing subtle group differences typically observed in psychotherapy clinical trials. Cohen (1992) distilled the findings of decades of psychosocial research and arrived at a classification of a —small effect (0.20 standardized mean difference), a —medium effect (0.50 difference), and a —large effect (0.80+ difference). This —small difference is also a sensible assumption, due in part to the small group differences in some of the psychosocial outcomes in our pilot IMCP trial (Table 1, e.g., psychological distress). Thus, we planned to have a sufficiently large sample size to detect subtle differences. Overall, this conservative estimate would accommodate outcomes in psychological distress which our pilot data showed a small difference. Based on these assumptions, we would need 104 participants in each arm at post-intervention (week 7) in order to obtain a power of 0.80. Other assumptions that go into this estimation included two *a priori* contrasts (IMCP vs. EUC and IMCP vs. ISP), and a two-sided, type-I error rate of 0.01 in the MANOVA test. The statistical power calculations were obtained from the computer program G*Power version 3.1 (Faul, Erdfelder, Lang & Buchner, 2007), for a MANOVA model with six correlated outcome variables. The output of the G*Power estimate is included below.

F tests – MANOVA: Global effects

Options : Pillai V, O'Brien–Shieh Algorithm

Analysis : A priori: Compute required sample size

Input:	Effect size $f^2(V)$	= 0.20
	α err prob	= 0.01
	Power (1– β err prob)	= 0.80
	Number of groups	= 2
	Response variables	= 6

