Output:	Noncentrality parameter λ	= 20.8000000
	Critical F	= 2.9936309
	Sample size	= 104
	Actual power	= 0.8062691
	Pillai V	= 0.1666667

A sample size of 104 per randomization arm (138 at baseline) at post-intervention would accommodate a post-intervention attrition rate of up to 25%, which is within the attrition rate in our pilot IMCP trial. The estimated sample size at the follow-up time point (week 15) is 90 participants per intervention condition.

Based on our current IMCP Group psychotherapy intervention, we are currently recruiting at a rate of 5 – 6 individuals to participate. This study involves the IMCP individual therapy, which is more flexible in terms of enrolling patients quickly and scheduling for starting of the therapy sessions. Thus we are confident that we will be able to recruit at a rate of 8 – 9 individuals per month and complete the total enrollment of 414 within the 4-year recruitment period.

Data analytic plans for the secondary aims

To examine clinical and demographic variables that may correspond to differential responses to Individual Meaning-Centered Psychotherapy (e.g., potential moderating influences such as gender, race/ethnicity, religiosity, level of pre-intervention social support, optimism, physical symptom burden, prognostic awareness, and treatment dose).

We anticipate that several socio-demographic and clinical variables will moderate the impact of IMCP. For example, we expect that level of religiosity (based on the IE-12) at the baseline/pre-intervention assessment will be inversely related to treatment response (i.e., less religious individuals will be more likely to experience benefits from this intervention than more religious individuals). We also predict that level of social support will moderate improvement, with those patients reporting higher levels of social support receiving the greatest benefits (because of the emphasis on connectedness to others as a source of meaning in the IMCP intervention). On the other hand, we expect that patients with poorer physical functioning (e.g., lower Karnofsky score), greater pain severity and overall symptom burden (MSAS Global Distress Index scores) will be less likely to benefit from the interventions, in part because unmanaged physical symptoms may impede participation.

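### The planned 0.20 standardized mean difference was entered in G*Power as f²(V) = 0.20, and a total of 104 was read as 104 per arm; power at the stated effect is about 5%, not 80%

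*Combined protocol and SAP*

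**What the plan says.** The sample size subsection of Section 11.0 states that the authors "based our sample size calculations on a 0.20 standardized mean difference in the MANOVA canonical variates between the IMCP and ISP interventions". It places 0.20 on Cohen's scale of mean differences (0.20 small, 0.50 medium, 0.80 and above large), describes the choice as conservative, and points to pilot Table 1 in support. It then says "we would need 104 participants in each arm at post-intervention (week 7) in order to obtain a power of 0.80", assuming two a priori contrasts (IMCP vs EUC and IMCP vs ISP) and a "two-sided, type-I error rate of 0.01 in the MANOVA test".

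The G*Power listing printed beneath has the input line "Effect size $f^2(V)$ = 0.20", with two groups and six response variables. Its output is λ = 20.8, critical F = 2.9936309, sample size 104, actual power 0.8062691 and Pillai V = 0.1666667. The text then carries 104 forward as a per-arm figure: "A sample size of 104 per randomization arm (138 at baseline) at post-intervention would accommodate a post-intervention attrition rate of up to 25" per cent. The enrolment of 138 per arm and 414 overall rests on that. Earlier in Section 11.0 the primary test is defined as a single omnibus MANOVA across all three arms.

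**The concern.** The prose and the software input use the same number, 0.20, for two different effect measures. A standardized mean difference is a distance in SD units; f²(V) is a ratio of explained to unexplained multivariate variation and grows with the square of that distance. The documents show no conversion between them. Separately, the printed noncentrality equals 104 × 0.20 exactly, which suggests that 104 is the total sample of the run rather than the size of one arm.

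The plan calls IMCP vs ISP the more important of its two hypotheses and says the sample is large enough for subtle differences. If the conversion is wrong, that claim is wrong, and anyone weighing a non-significant IMCP vs ISP result would have the wrong figure for what the trial could detect.

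**Working it through.** **Inputs (all from Section 11.0).** Two groups, p = 6 outcomes, alpha 0.01, f²(V) = 0.20 as entered, 0.20 SD as described, 104 evaluable per arm as read by the plan.

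**Formulas.** With two groups the MANOVA has one canonical variate. Then Pillai V = f²/(1 + f²), df1 = 6, df2 = N − 7, λ = N × f², where N is the total over both groups. For equal groups f² = D²/4, where D is the Mahalanobis distance, that is, the standardized mean difference on the canonical variate.

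**Step 1: reproduce the printed output.** With N = 104 in total and f² = 0.20:
- V = 0.20/1.20 = 0.1666667
- λ = 104 × 0.20 = 20.8
- df = (6, 97), critical F = 2.9936309
- power = 0.8062691

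Every printed value matches. With N = 208 (104 per arm), λ would be 41.6, critical F 2.8928 and power 0.997, none of which was printed. So 104 is the total, or 52 per arm.

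**Step 2: convert the effect sizes.**
- f² = 0.20 gives D = 2 × √0.20 = 0.894.
- D = 0.20 gives f² = 0.04/4 = 0.01, one twentieth of what was entered.

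**Step 3: separate the two errors.** Power at alpha 0.01:

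| Total N in the two arms | f² = 0.20 (D = 0.89) | f² = 0.01 (D = 0.20) |
|---|---|---|
| 104 (52 per arm) | 80.6% | 2.3% |
| 208 (104 per arm) | 99.7% | 4.5% |

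The lower right cell is the design as described: λ = 208 × 0.01 = 2.08, df = (6, 201), power 4.5%. A simulation of 20,000 two-sample Hotelling tests gave 4.7%. Reading the total as per arm raises power; the effect-size error alone causes the collapse. With all 138 per arm and no attrition (N = 276), power is 6.3%.

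**Step 4: what would be needed, and what 104 per arm delivers.** For 80% power at D = 0.20 the two arms need 1,896 patients, or 948 each. With 104 per arm, 80% power is reached at D = 0.615, f² = 0.615²/4 = 0.095.

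**Step 5: other readings of 0.20 (104 per arm, alpha 0.01 unless stated).**
- Cohen's f = 0.20, so f² = 0.04: 29.5%.
- D = 0.20 at alpha 0.05: 14.7%.
- t-test on a single composite at 0.20 SD: 12.6%.
- All six outcomes shifted by 0.20 SD with common correlation ρ, so D² = 0.24/(1 + 5ρ): 51% at ρ = 0, 19% at 0.2, 9% at 0.5, 6% at 0.7. The documents give no correlation, so ρ is an assumption; Section 11.0 describes the outcomes as highly correlated, which points to the lower figures.

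**Step 6: the three-arm omnibus (312 evaluable).** Power depends on where EUC lies, which the documents do not say. Assuming IMCP − ISP = 0.20 and all three means on one line, it is about 3% with EUC midway, 4% with EUC level with either arm, 19% with EUC 0.20 below ISP and 85% with EUC 0.50 below ISP.

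**The case against.** Several points can fairly be made for the plan.

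- **The literal reading is the harshest.** Treating 0.20 as the canonical distance gives 4.5%, and other readings give more. This is true, but the plan names the canonical variate itself, and no reading of the two-arm contrast in Step 5 exceeds 51%.
- **The two-group run fits the stated contrasts.** The sizing paragraph says it rests on two pairwise comparisons, so two groups is not in itself an error. This stands. What remains is that no power is given for the three-arm omnibus, which is the primary test. Omnibus power could be high if EUC did much worse than the other arms, but that would say nothing about IMCP vs ISP.
- **The pilot does show small group differences in distress.** The text under *Pilot Study of IMCP* in Section 3.0 reports between-arm HADS comparisons that were not significant (anxiety p = .47, depression p = .63). This also stands: the fault is in citing Table 1, whose note defines d as change from baseline within the IMCP arm.
- **The trial is not weak for every effect.** It has 80% power at about 0.62 SD, and the enrolment need not be called inadequate for differences of that size. The documents also set no rule for interpreting a null result, so the defect is the stated power claim, not a stated misinterpretation.

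**Conclusion.** The concern holds. The plan's own output proves both errors: it reproduces to the last printed digit only with f²(V) = 0.20 and 104 patients in total. The claim of 80% power for a small difference is wrong by a wide margin: about 5% on the plan's wording, and between about 5% and 51% across the readings of the two-arm contrast considered. The 4.5% figure assumes equal arms, multivariate normal outcomes with a common covariance matrix, and 104 evaluable patients in each. The six-outcome range also assumes a common correlation, and the omnibus figures assume a position for EUC; neither assumption is needed for the main conclusion.

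**What to change.** Keep the enrolment and correct the text of Section 11.0.

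1. State that, with 104 evaluable per arm, each two-arm six-outcome contrast at alpha 0.01 has 80% power for a canonical (Mahalanobis) difference of about 0.62 SD (f² about 0.095) and about 5% power for 0.20 SD.
2. Delete the statements that the size is based on a small 0.20 standardized mean difference, is conservative, and suffices for subtle differences.
3. State that the G*Power figure of 104 was the total over two groups. The per-arm 104 should then stand on the restated detectable difference.
4. Stop citing Table 1 as evidence on group differences; if pilot support is wanted, cite the between-arm HADS results in Section 3.0.
5. Label the restated power as applying to two-arm contrasts. Any figure for the three-arm omnibus should come with its assumption about EUC.

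The cost is protocol and SAP wording only. No patients are added and the analysis does not change, but the stated detectable effect becomes less favourable.

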.26 - .46), $t = 3.48$, $p = .0008$ and $b = 0.39$ (95% CI: 0.05 - 0.72), $t = 2.27$, $p = .03$, respectively. There were also significantly greater benefits for IMCP, compared to TM, in improving overall quality of life (MQOL), $b = 0.70$ (95% CI: 0.17 - 1.24), $t = 2.58$, $p = .02$, decreasing the number of physical symptoms endorsed (MSAS-Sx), $b = 4.66$ (95% CI: 1.53 - 7.79), $t = 2.92$, $p = .005$, and decreasing severity of physical symptom distress (MSAS-GDI), $b = 0.42$ (95% CI: 0.20 - 0.64), $t = 3.77$, $p = .0003$. There were no significant differences between these two interventions in terms of reducing anxiety (HADS-A), $b = 0.04$ (95% CI: -0.13 - 0.06), $t = -0.72$, $p = .47$, depression (HADS-D), $b = 0.03$ (95% CI: -0.09 - 0.14), $t = 0.49$, $p = .63$, or hopelessness (BHS), $b = .13$ (95% CI: -0.27 - 2.52), $t = 1.59$, $p = .12$.

In order to examine the basis for the group differences, simple change scores within each treatment arm were analyzed, along with paired t-tests to determine whether the change on each measure was significantly greater than zero. As evident in Table 1, participants in the IMCP arm demonstrated significant reductions in symptoms and improvement in quality of life/spiritual well-being across most of the study variables. Although many (but not all) of the effect sizes decreased somewhat during the follow-up period, most of these change scores remained significant. However, there was a markedly different pattern for participants receiving TM, with very few significant improvements (only hopelessness improved significantly following the TM intervention) at either the end of treatment at the 2-month follow-up.

We followed a similar approach for the analysis of the long-term benefits of treatment, using repeated measures ANOVA models to evaluate the differential impact of treatment on spiritual well-being and psychological functioning at the 2-month follow-up assessment. As with the post-treatment analyses, treatment arm was entered as a categorical independent variable and baseline score on the outcome variable was entered as a co-variate. These analyses revealed no significant differences in treatment efficacy for IMCP versus TM at the 2-month follow-up assessment, although a similar pattern of improvement was evident in the within-group analyses.

Table 1: Changes in Spiritual Well-being and Psychological Functioning Following IMCP

	M Pre	M Post	d	p	M F/U	d	p

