Spiritual Well-being							
FACIT Total	2.24	2.72	1.21	.0001	2.60	0.69	.0005
Meaning/Peace	2.49	2.98	1.01	.0001	2.78	0.53	.006
Faith	1.69	2.15	0.66	.0002	2.25	0.63	.002
Psychological Functioning							
Anxiety	2.39	2.24	0.22	.17	2.16	0.48	.02
Depression	2.09	1.98	0.22	.18	1.89	0.51	.07
Hopelessness	7.57	4.70	0.80	.0001	4.84	0.63	.002
Physical Functioning/QOL							
Overall Quality of Life	5.89	7.18	0.94	.0001	6.88	0.71	.0003
Number of Symptoms	18.7	16.0	0.32	.06	17.5	0.14	.42
Symptom Distress	1.95	1.53	0.79	.0001	1.84	0.22	.22

Note: *M* pre: group mean at baseline; *M* post: group mean at end of treatment; *M* F/U: group mean at 2-month follow-up assessment;
 d , p correspond to effect size for comparison to baseline score (*M* pre)

Table 1 reveals that the therapeutic benefits of IMCP were somewhat more modest at the 2-month follow-up, but remained strong and statistically significant for most variables. In fact, some variables demonstrated more substantial improvements at the follow-up assessment (i.e., anxiety and depression). No such changes were evident in the TM treatment arm, with the —null findings continuing at the 2-month follow-up assessment.

Conclusions: IMCP appears to be a potentially beneficial intervention for patients' emotional and spiritual suffering at the end of life. Participants who received IMCP demonstrated substantial

and statistically significant improvements in spiritual well-being, a sense of meaning, hopelessness, overall quality of life, and symptom-related distress, and more modest effects for anxiety, depression and symptom burden. These treatment gains were sustained at the follow-up assessment, 2 months after completion of treatment. Patients who received TM, on the other hand, demonstrated little improvement in these outcome variables. When comparing the effects of these two treatments, IMCP resulted in significantly greater improvements in a number of variables studied. Further research that compares IMCP with other psychotherapeutic interventions, such as this current larger randomized control trial and includes a non-active control group, is needed to better understand the unique benefits of this treatment approach.

Potential Advantages of IMCP for Advanced Cancer Patients

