11.0 BIOSTATISTICS

This project involves a parallel-arm randomized controlled clinical trial to compare the efficacy of three psychotherapy interventions: 1) Individual Meaning-Centered Psychotherapy (IMCP); 2) Supportive Individual Psychotherapy (ISP); and 3) Enhanced Usual Care arm (EUC). We plan to recruit altogether 414 patients (138 in each arm) with solid tumors with advanced disease. The primary outcomes include assessments of meaning (LAP-R), spiritual well-being (FACIT-Sp) and psychological distress (HADS, SAHD, HAI, MQOL).

Omnibus MANOVA for the primary aim:

The general paradigm for assessing the outcomes will be multivariate analysis of variance (MANOVA). MANOVA is appropriate because the primary psychosocial outcomes are highly correlated. The MANOVA method essentially combines the multiple dependent variables together into a weighted linear combination of canonical variates. The canonical coefficients provide the weights in this linear combination. The canonical weights have several advantages. The main advantage is that they inform the relative contribution of each outcome to the overall canonical function (i.e., whether or not meaning contributes more than spiritual well-being to the overall canonical function). MANOVA was chosen, rather than, for example, a mixed-effects modeling approach, primarily because of these considerations. In MANOVA, the combined canonical variate is analyzed in a manner similar to a univariate ANOVA.

The primary aim of this study will be evaluated in one omnibus, one-way MANOVA model against the null hypothesis that all three randomized arms entail comparable post-intervention outcomes in meaning, spiritual well-being, and psychological distress. Thus, the dependent variables will be the six primary outcome assessments (LAP-R, FACIT-Sp, HADS, SAHD, HAI, and MQOL) measured at the post-intervention time point (week 7). The sole independent variable is the randomized intervention assignment. Dunlop, Cortina, Vaslow & Burke (1996) showed that this method provides the most generalizable findings, findings that do not depend on the patients' baseline scores or other baseline characteristics. Thus, the omnibus MANOVA will test whether or not the psychotherapy groups differ in all six correlated outcomes of interest.

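### The 0.20 planning effect is said to cover psychological distress on the strength of pilot Table 1, which holds no between-arm differences; the pilot neither supports nor refutes 0.20 for the HADS, and power for a 0.20 SD difference on one scale is 13%

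*Combined protocol and SAP*

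**What the plan says.** The sample-size part of Section 11.0 plans on a "0.20 standardized mean difference in the MANOVA canonical variates between the IMCP and ISP interventions", with "a two-sided, type-I error rate of 0.01 in the MANOVA test", 80% power and 104 patients per arm at week 7. It gives two grounds for 0.20. The first is Cohen's label for a small effect. The second is the pilot: the value is called sensible "due in part to the small group differences in some of the psychosocial outcomes in our pilot IMCP trial (Table 1, e.g., psychological distress"). It then concludes that "this conservative estimate would accommodate outcomes in psychological distress which our pilot data showed a small difference".

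Table 1 is in Section 3.0 under the IMCP pilot study. Its title refers to changes after IMCP, it carries one set of means, and its note says that d and p "correspond to effect size for comparison to baseline score (*M* pre"). The preceding text introduces it with within-arm change scores and paired t-tests.

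The pilot's between-arm comparisons, IMCP against therapeutic massage, are in that same text: "There were no significant differences between these two interventions in terms of reducing anxiety (HADS-A") or, as the sentence continues, depression or hopelessness.

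The primary analysis takes six outcomes "measured at the post-intervention time point (week 7). The sole independent variable is the randomized intervention assignment". Sections 9.1 and 11.0 list HADS, SAHD, HAI and MQOL under psychological distress.

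**The concern.** A within-arm change from baseline is not evidence about the difference between two randomized arms. It includes whatever change would have occurred without IMCP, and it may be scaled by a different standard deviation. The one distress entry in Table 1 that looks like 0.20 is d = 0.22 for anxiety and for depression after treatment, so a reader could easily take it as the pilot's estimate of the quantity being planned for.

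At stake is how a null HADS result will be read. The plan tells the reader that the trial was sized with distress in mind at 0.20. If power for that difference on a distress scale is low, a non-significant HADS comparison could be mistaken for evidence of no benefit.

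**Working it through.** **The plan's own figure.** For a two-group MANOVA with 6 outcomes, df1 = 6, df2 = N - 7 and lambda = N × f². With "Effect size $f^2(V)$ = 0.20", alpha 0.01 and N = 104: lambda = 104 × 0.20 = 20.8, critical F = 2.9936, power = 0.8063. This matches the printed output. In that calculation 104 is the total over two groups, and f² = 0.20 corresponds to a multivariate distance of sqrt(4 × 0.20) = 0.89. That is a separate matter from the source of the 0.20, but it means that the output is no evidence of 80% power at a standardized difference of 0.20.

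**Units of d in Table 1.** The SD used is not stated. If d is change divided by the SD of change, the paired t is d × sqrt(n). The n that gives the printed post-treatment p is:

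| Row | d | p | n |
|---|---|---|---|
| Anxiety | 0.22 | .17 | 40.4 |
| Depression | 0.22 | .18 | 38.6 |
| Number of symptoms | 0.32 | .06 | 36.8 |
| Faith | 0.66 | .0002 | 38.9 |

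This fits the 39 IMCP patients who attended all seven sessions. A two-independent-samples d would need 67 to 79 per time point, more than the 59 who began IMCP. So d is very probably in SD-of-change units. On the raw-score scale, 0.22 becomes 0.22 × sqrt(2(1 - r)): 0.26 at r = 0.3 and 0.17 at r = 0.7, where r is an assumed pre-post correlation.

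**Between-arm effects.** d ≈ t × sqrt(1/n1 + 1/n2). The analysed n is not given. I take 59/54 (59 who began IMCP, 54 randomized to massage) to 39/33 (those who attended all sessions), so the multiplier runs from 0.188 to 0.237.

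| Measure | t | d at 59/54 | d at 39/33 |
|---|---|---|---|
| HADS-A | -0.72 | -0.14 | -0.17 |
| HADS-D | 0.49 | 0.09 | 0.12 |
| Hopelessness (BHS) | 1.59 | 0.30 | 0.38 |
| MQOL | 2.58 | 0.49 | 0.61 |

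The pilot models adjusted for baseline, so these are approximate and in residual-SD units.

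Approximate 95% limits are (t ± 1.98) × multiplier. HADS-D: -0.28 to 0.47 at 59/54 and -0.35 to 0.58 at 39/33. HADS-A: -0.51 to 0.24 and -0.64 to 0.30. All include 0.20.

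The HADS-A line is internally inconsistent: b is printed as 0.04, but t is -0.72 and the interval (-0.13 to 0.06) is centred at -0.035.

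**Single-scale power, 104 per arm (noncentral t, two-sided).**

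| True difference (SD) | alpha 0.01 | alpha 0.05 |
|---|---|---|
| 0.22 | 16% | 35% |
| 0.20 | 13% | 30% |
| 0.12 | 4% | 14% |

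The difference detectable with 80% power is about 0.48 SD at alpha 0.01 and 0.39 SD at 0.05. The normal approximations are (2.576 + 0.842) × sqrt(2/104) = 0.47 and (1.960 + 0.842) × sqrt(2/104) = 0.39.

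**The case against.** The strongest reply has four parts.

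- Table 1 is only a secondary ground; Cohen's small effect comes first. That is true, but a generic label cannot support a statement about what the pilot showed for distress.
- Distress is broader than the HADS. This stands. Hopelessness and MQOL both exceed 0.20 between arms. The transfer is imperfect: the pilot used the BHS where this trial uses the HAI, and its reported results include no SAHD.
- The 0.20 is placed on the canonical variates, where separation is at least as large as on any one included scale, and the pilot's between-arm FACIT-Sp result (t = 3.74, about 0.70 to 0.88 by the same conversion) is far above it. This stands too: on that scale, the word conservative is unproven against ISP, not shown to be false.
- Alpha 0.01 is set for the MANOVA, and no test of a single HADS score at 0.01 is specified; individual outcomes may use a false-discovery-rate procedure. This is why both alpha levels are given. Single-scale power is low even at Table 1's own 0.22, so the miscitation did not cause the shortfall.

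A reader might infer that the pilot showed distress effects that were reversed, or too small for 0.20 to be plausible. The documents do not support that. Only the HADS results are near zero, the HADS-A sign rests on t and an interval that conflict with the printed b, and the intervals include 0.20.

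**Conclusion.** The citation is wrong: Table 1 cannot support a between-arm planning value. The between-arm pilot results that should have been cited are mixed across the distress measures and uninformative about 0.20 for the HADS. The statement that the sample size accommodates distress at 0.20 is therefore unsupported for the HADS. It is also misleading about any single distress scale, where power at 0.20 SD is 13% (30% at alpha 0.05).

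These power figures assume 104 analysed per arm, a two-arm comparison and a difference in SDs of the week-7 score. They should not be read as the power of the omnibus test, which depends on all six outcomes and their correlations. The pilot effect sizes rest on the assumed analysed numbers and on a massage comparator, so they do not estimate the IMCP-ISP difference.

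**What to change.** In the sample-size part of Section 11.0:

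1. Replace the reference to Table 1 with the between-arm results from the Section 3.0 pilot text. Give the analysed n, note that the comparator was massage, and reconcile the HADS-A b with its t and interval.
2. Remove the claim that the sample size accommodates a 0.20 difference in distress, naming the HADS specifically.
3. State instead that at 104 per arm a single scale has 80% power for about 0.48 SD at two-sided alpha 0.01 (0.39 SD at 0.05), and 13% power (30%) at 0.20 SD. Label these as single-scale figures, not the power of the MANOVA.

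The cost is rewording and a less favourable stated figure. No patients, data or analyses are added.

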2.1 OBJECTIVES AND SCIENTIFIC AIMS

Primary Aim:

- To conduct a randomized controlled trial comparing the efficacy of Individual Meaning-Centered Psychotherapy (IMCP), a standardized Individual Supportive Psychotherapy (ISP) and Enhanced Usual Care (EUC) in improving meaning and spiritual well-being and overall quality of life and reducing psychological distress (depression and anxiety, hopelessness and desire for hastened death) in a sample of patients with advanced cancer.

Secondary Aims:

- To examine clinical and demographic variables that may correspond to differential responses to Individual Meaning-Centered Psychotherapy (e.g., potential moderating influences such as gender, race/ethnicity, religiosity, level of pre-intervention social support, optimism, physical symptom burden, prognostic awareness, and treatment dose).
- To assess the relative impact of Individual Meaning-Centered Psychotherapy on different aspects of meaning (e.g., purpose, coherence, existential vacuum), as well as on different aspects of spiritual well-being (meaning versus faith),
- To explore whether an enhanced sense of meaning —explains|| (mediates) improved psychological well-being (i.e., increased quality of life, decreased psychological distress).

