Analyses: Putative explanatory covariates will be identified and tested statistically using the method originally described by Baron and Kenny (1986), and more recently by MacKinnon (2008). Specifically, these will involve Multi-Variate Analysis of Covariance (MANCOVA) using the changes in the six primary outcomes (post intervention minus baseline) as a function of intervention condition, controlling as covariates the effects of gender, race/ethnicity, and baseline covariates in religiosity, social support, optimism, physical symptom burden, pain severity, and overall symptom burden. This analytic approach entails the following advantages: 1) change scores have the advantage of clearly identifiable direction of change, 2) psychosocial outcomes are measured on an interval scale (such as measures of temperature in the Fahrenheit or Celsius scales), so that change scores are less prone to problems associated with respondents using different internal psychological scales; and 3) precedence exists (Flay et al. 1995) in interventions designed for behavioral change. This method offers several advantages, both in terms of power as well as interpretation, to a traditional repeated measures design for analyzing data when both independent and dependent variables are assessed at two or more time points (Huck & McLean, 1975; Willet, 1988-9). Change score analyses will include the baseline score as a covariate if change is significantly correlated with baseline score (as is often the case).

To assess the relative impact of Individual Meaning-Centered Psychotherapy on different aspects of meaning (e.g., purpose, coherence, existential vacuum), as well as on different aspects of spiritual well-being (meaning versus faith):

Two additional MANOVA models will be carried out. In the first model, pre-post change scores of different aspects of meaning (e.g., purpose, coherence, existential vacuum) will be modeled by intervention conditions to examine the relative impact of IMCP on these outcomes. The canonical weights will be used to estimate the relative contribution of each mean components on the overall canonical function. Components of spiritual well-being will also be analyzed similarly, in a separate MANOVA model. Univariate ANOVA contrasts will be used to compare IMCP against ISP and IMCP against EUC.

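### The moderator analysis has no arm-by-moderator term, so the planned MANCOVA cannot test or estimate differential response to IMCP

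*Combined protocol and SAP*

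**What the plan says.** The first secondary aim in Section 2.1 concerns "potential moderating influences such as gender, race/ethnicity, religiosity, level of pre-intervention social support, optimism, physical symptom burden, prognostic awareness, and treatment dose". Section 11.0 (Data analytic plans for the secondary aims) repeats the aim and adds: "We anticipate that several socio-demographic and clinical variables will moderate the impact of IMCP". It then gives directions. Less religious patients should gain more, patients with more social support should gain most, and patients with poorer Karnofsky scores, more pain or more symptoms should gain less.

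The analysis paragraph that follows cites two methodological references. It then sets out the model, a MANCOVA of pre-to-post change in the six primary outcomes "as a function of intervention condition, controlling as covariates the effects of gender, race/ethnicity, and baseline covariates in religiosity, social support, optimism". The covariate list closes with pain and two symptom-burden terms. One further term is conditional: "Change score analyses will include the baseline score as a covariate if change is significantly correlated with baseline score". It too is a main effect.

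No product term, subgroup contrast or arm-specific slope appears anywhere in Section 11.0. The later mediation paragraph has none either.

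**The concern.** Moderation means that the difference between arms changes with a patient characteristic. A model that enters the characteristic only as a covariate estimates how that characteristic relates to change across IMCP, ISP and EUC together, which is prognosis. A religiosity coefficient from this model would say whether religious patients change more or less whatever arm they are in. It would not say whether IMCP works better for the less religious.

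Two errors could follow. A covariate that is only prognostic could be reported as a moderator, and a real moderator could be missed. In either case an aim with stated directional hypotheses goes unanswered.

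The model also does not match the aim. Prognostic awareness and treatment dose are named in the aim but are not among the covariates, and Karnofsky score is in the predictions but not in the model. Treatment dose is in any case a different kind of variable: it arises after randomisation, and EUC has no sessions.

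**Working it through.** **1. The plan's own figure.** Section 11.0 gives no effect size, power or sample size for the moderator analysis, so the only figure to reproduce is the primary one, which assumes "a two-sided, type-I error rate of 0.01 in the MANOVA test". Inputs from the G*Power listing: 2 groups, 6 outcomes, f²(V) = 0.20, alpha 0.01. With N = 104, λ = 104 × 1 × 0.20 = 20.8, df = 6 and 97, critical F = 2.9936 and power = 0.8063, as printed. N in that calculation is the total over two groups. Below I use 104 per arm because the plan states it as the analysed number after 25% attrition (138 × 0.75 = 103.5).

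**2. The algebra.** For one outcome and one moderator M, the written model is

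E(change) = α + β₁·IMCP + β₂·ISP + γM.

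The IMCP–EUC difference is β₁ and the IMCP–ISP difference is β₁ − β₂, at every value of M. The coefficient γ is one slope shared by all arms. A model for moderation adds δ₁·IMCP·M + δ₂·ISP·M. The IMCP–EUC difference is then β₁ + δ₁M, and the IMCP–ISP difference is (β₁ − β₂) + (δ₁ − δ₂)M. The aim is about δ₁ and δ₁ − δ₂, and neither is in the written model.

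**3. Illustration by simulation.** From the plan: three arms, 104 per arm, six outcomes. Assumed: one standardised continuous moderator, outcome correlation 0.5, no average arm effect, alpha 0.05, slopes in SD of outcome per SD of moderator and equal for all six outcomes. Pillai tests, 2,000 runs per row.

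| True situation | Arm test (written model) | Covariate test (written model) | Arm × moderator test (added) |
|---|---|---|---|
| No effect | 4.6% | 5.0% | 5.2% |
| Prognostic only, slope 0.4 in all arms | 5.4% | 100% | 4.4% |
| Moderation, slope difference 0.3, average slope 0 | 4.6% | 5.8% | 51% |
| Moderation, difference 0.4, average slope 0 | 4.4% | 5.4% | 79% |
| Moderation, difference 0.5, average slope 0 | 4.8% | 5.0% | 97% |
| Slope 0.4 in IMCP only | 4.6% | 58% | 83% |

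In the last row the covariate test often rejects because the average slope is 0.4/3 = 0.13. It cannot distinguish that from a prognostic slope of 0.13 in all arms.

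**4. Precision of the corrected analysis.** For one outcome, IMCP versus ISP, 208 patients, arm coded ±0.5 and a continuous moderator with SD 1, the interaction SE is 1/√(208 × 0.25) = 0.139. At alpha 0.05, power is Φ(0.5/0.139 − 1.96) ≈ 95% for a slope difference of 0.5 and Φ(0.3/0.139 − 1.96) ≈ 58% for 0.3. For seven moderators and two contrasts, a Bonferroni level of 0.05/14 lowers these to about 76% and 23%. False discovery rate (FDR) control would fall between the two sets of figures.

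For a binary moderator split 50/50, the interaction SE is √(4/52) = 0.277, against √(2/104) = 0.139 for the arm effect. The difference detectable with 80% power is (1.960 + 0.842) × 0.277 = 0.78 SD, against 0.39 SD.

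**The case against.** The best reply is that an interaction was intended. The paragraph cites the Baron–Kenny method, and the title listed in Section 16.0 refers to the distinction between moderators and mediators. That makes an oversight plausible. It does not settle the matter, because the next sentence of the plan defines the model, and what it defines is covariate adjustment. If an interaction was meant, it still has to be written, together with the moderators, contrasts and multiplicity rule.

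Several smaller points stand:

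- The plan does not say that a significant covariate will be reported as a moderator, so misreporting is a risk and not a certainty.
- The list of moderators is illustrative, so the omission of prognostic awareness is an inconsistency rather than a breach.
- The plan never calls treatment dose a baseline moderator, and a reading confined to the therapy arms is possible.
- The symptom-burden prediction refers to the interventions in the plural, so it does not clearly imply an IMCP-versus-ISP interaction.
- The simulation shows an algebraic fact under assumed slopes. It does not measure a loss in this trial.

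**Conclusion.** The concern holds. As written, the moderator analysis contains no parameter for differential response, so the first secondary aim cannot be answered. This follows from the form of the model and needs no numerical assumption. The rejection rates, 100% for a purely prognostic covariate and 5.0–5.8% for moderation with slopes averaging zero, depend on the assumed slopes, the correlation of 0.5, the single moderator and alpha 0.05.

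The effect is confined to a secondary aim; the primary MANOVA is untouched. It should be corrected, but it does not threaten the trial's main conclusion.

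**What to change.** In Section 11.0, list the baseline moderators and fit arm × moderator terms for each, with IMCP versus ISP and IMCP versus EUC as the contrasts. Centre continuous moderators, keep all main effects, and always include the baseline outcome. Report each interaction with its confidence interval. Extend the FDR procedure, which the plan already names for the individual outcomes, across moderators and contrasts.

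Reconcile the list with the aim and the predictions by adding prognostic awareness and Karnofsky score. For prognostic awareness use the T1 self-report part, because Section 7.1 has the other part rated by the therapist and EUC has no study therapist. Questionnaire moderators are collected at T1, after allocation is disclosed but before the first session (Sections 4.2 and 7.1), so describe them as pre-treatment.

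Take treatment dose off the moderator list and report it as an exploratory dose-response analysis within IMCP and ISP.

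The cost is SAP wording and a few model terms, with no new data. The interaction estimates will be less precise than the arm effects (twice the SE for an evenly split binary moderator), so they should be labelled exploratory.
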